2. Women who enrolled and completed all parts of the NEST study (IRB #17-987)
3. In the 3rd trimester of pregnancy or delivered within the past 12 months
4. Able to read and speak English
5. Able to provide consent for research participation

Exclusion Criteria:

1. Women younger than 18 years of age
2. Women who were withdrawn from the NEST study as a result of an obstetrical (e.g., miscarriage or pregnancy loss, IUDF, premature delivery) complication
3. Women who withdrew themselves from the NEST study
4. NEST participants who already were recontacted about an interview at an earlier stage in the study
5. Unable to read or speak English
6. Unable to provide informed consent for research participation

Sample size: We will have a target sample size of 40 participants for the in-depth interviews. Based on our prior studies, we anticipate this will be the number at which saturation will be achieved with respect to identification of lead decision-making factors. Interim analysis will be used to determine if additional interviews need to be conducted. Final sample size will be determined by the point at which theoretical saturation has been met.

Recruitment:

We will contact participants who meet the above inclusion criteria regarding participation in in-depth telephone interviews via MyChart or email, whichever has been the approved method (by the participant) for contact as part of the NEST study.

Before re-contacting is initiated, a research team member will review to determine if individuals meet inclusion criteria. This will include a review of 1) the medical record of eligible participants to determine if any obstetrical complication has occurred that would constitute exclusion and 2) the research documentation to determine if an eligible participant withdrew or was withdrawn from the NEST study. Additionally, we will not re-contact participants who may have taken part in an interview done at an earlier time in the study. These individuals will not be re-contacted.

The research team member will send those women who meet inclusion criteria a recruitment letter that describes the study and directions to contact the Research Coordinator (by email, telephone, or MyChart response) if interested in study participation. This letter will be sent via MyChart or email, whichever has been the approved method (by the participant) for contact as part of the NEST study.

The Research Coordinator will document the date of first re-contact. The eligible participant will be sent a follow up message within one week via the preferred contact method documented as part of the NEST study if no response regarding participation has been received. A second follow up message will be sent via the preferred contact method if no response has been received within 7 days of the prior contact. No additional attempts to reach the eligible participant will take place after this point.

Informed consent procedures:

Informed consent will be obtained prior to data collection for this phase of the NEST study. Written informed consent will be obtained prior to data collection. In developing this informed consent process, we are cognizant of the importance to not have patients present for research outside of their scheduled visits and to reduce potential exposure. The informed consent will be obtained via DocuSign (Part 11 Compliant).

The process of obtaining consent will be as follows: Once the eligible participant contact the Research Coordinator, and expresses their interest, the coordinator will send the participant a copy of the informed consent (this will be sent via email or USPS, based on the participant's preferences). After an initial review by the patient, a telephone call will take place between the patient and the Research Coordinator to formally review the consent form and detail the patient's responsibilities as the research participant. Following that phone call, if the patient still wants to participate, the research coordinator will then provide instructions on how the patient will sign the consent via the DocuSign platform (instructions on how to use DocuSign will be sent to the participant). After the document has been signed by all parties, the patient will receive an email notification that the document is complete. The notification will include the completed tamper-sealed PDF as an attachment. Once the consent is signed by both the participant, the Research Coordinator will make sure, (1) a copy of the consent will be sent back to the participant for her records, (2) the signed consent (physical copy) will be kept in a locked file in the Women's Health Institute, and (3) an electronic copy will be saved on the secured WHI shared drive.

Once the informed consent is completed, the patients name and contact will be sent to [name], study PI, who will work with the patient to schedule time for the telephone interview. Prior to the interview, [name] will confirm that the participant understands the nature of the study and is willing to participate in the study and will also confirm the participants identify by verifying their date of birth.

Data Collection:

[name] or a member of the research team will conduct a semi-structured interview with the participant. The interview will be structured using an interview guide. Questions will pertain to patient preference regarding the mode and timing of educational resources and decision-support tools used in place of or in conjunction with the NEST tool over the course of pregnant.

As part of the interview, we will ask participant their opinions on how best to support patients across the longitudinal experience of prenatal genetic testing, beginning in the first trimester with the initial decision to undergo testing and ending in the second trimester. To do so, we will ask

participants to review a diagram that provides an overview of the testing process during the interview and provide their feedback on the testing process and concurrent educational/decision support process (see Picture 1). We will instruct the participant to review the picture during the final set of questions. The interviewer will walk the participant through the different testing options, explaining some of the terms and abbreviations on the diagram, and emphasizing both the optional and preference-based nature of the process.

This diagram was developed in conjunction with [name], prenatal genetic counselor and study co-I, to reflect the testing algorithm in place at the Cleveland Clinic. We will ask participants to have this diagram (see below for how they will receive it) at the start of the interview, both when we are scheduling the interview and at the start of the interview process.

This diagram will be sent to the participant by one of these methods:

- 1) My email at their preferred email address: We will inform participants that they will receive an email with the subject line "Information for the study interview." The email will contain a brief message about the attachment and the instructions not to open the attachment until instructed so during the interview.
- 2) US postal mail: If the participant prefers the diagram to be send via US postal mail, we will mail a paper copy of the diagram in a sealed envelope with the accompanying letter with instructions.

We have also developed a plan if the participant does not have access to the paper or electronic diagram at the time of the interview. In this case, we will ask the participant if we may text a photo of the diagram to her phone. If the participant declines this option and does not want to reschedule the interview, we will not include the question pertaining to the diagram in the interview.

The interview will be audio-recorded for data analysis purposes. The research team member will take field notes during the interview for data analysis. Digital audio files will be immediately downloaded from the Research Compliance approved digital recording device to a secure folder on the WHI shared drive and then deleted from the audio device. This is the same procedure which was Research Compliance and IRB approved for the IRB study #19-139. Audio-recordings will be quality checked. Before the interview begins, participants will be asked not to include any personal identifying information during the interviews by using the IRB approved phone script. Any identifying information inadvertently disclosed by the participant during the interviews will be deleted from the original data file.

Interviews will last 30-45 minutes. Participation will end at the conclusion of the telephone interview. Participants will receive a \$50 gift card in appreciation of their time and effort with the study.

Data analysis:

Audio-recordings will be transcribed verbatim and verified for accuracy. The team will approach data analysis as an iterative and progressive process of data immersion, coding, memoing and theme identification, an inductive process consistent with grounded theory. We will identify

content domains and categories in transcripts to create a coding tree that will be used to organize the data. A companion codebook will be created to serve as a reference for analysis. Transcripts and coding tree will be uploaded to NVivo (version 12), a qualitative data management and analysis software package. The research team will hold weekly meetings to review data coding and memoing and identify themes. Themes identified will be contextualized with information about trimester of pregnancy, gravity/parity, and previous pregnancies. Demographic data will be utilized to provide clarification of how findings are predicted by these variables.

Data Access and Confidentiality:

Access to potentially identifiable research data will be restricted to members of the research team who are knowledgeable about applicable federal regulations and institution policies governing the involvement of human subjects in research. No participants will be identified by name in any research reports or publications about the study. Any personal identifying information inadvertently disclosed by the participant during the interview will be permanently deleted from the audio-file. In the informed consent document, all participants will be advised that their decision to participate is voluntary and responses will not be disclosed to anyone outside the research team.

Signed participant consent forms will be kept electronically on the secured WHI shared drive and physical copies will be stored in a locked file cabinet in the office of the Principal Investigator. Any field notes will be entered into the secured Cleveland Clinic REDCap and physical notes will be kept in a locked cabinet in the office of the NEST study team.

Only IRB approved research staff for this study will have access to this information. These data management practices will be used throughout the duration of data collection and data analysis. No participants will be identified by name in any research reports or publications about the study. All data will be destroyed when allowed by institutional regulations.

Data management:

Data from the interviews will be collected with field notes and entered using NVivo and Word. A master list used to track of inclusion criteria, informed consent, data collection, and the allocation of the participant stipend. These data will be saved on a restricted file of the WHI secure Cleveland Clinic drive.

All study information will be maintained in a secure fashion as delineated by the Cleveland Clinic IRB: either in a locked cabinet in the OB/GYN and Women's Health Institute or on a secure WHI shared drive accessible only by IRB approved research team members.

Only members of the research team will have the ability to access this information. Access to research data will be restricted to members of the research team who are knowledgeable about applicable federal regulations and institution policies governing the involvement of human subjects in research.

Adverse Events and Data Monitoring:

The Principal Investigator will meet with the research team on a weekly basis to monitor progress of the study and reassess the human subject protection procedures, subject eligibility, and data collection strategies.

Based on our prior research, we do not expect any major adverse events or unanticipated problems related to the subject safety.

The PI will monitor subject safety throughout the course of the study, and promptly communicate any unanticipated problems to the IRB and the NEST DSMB as this is part of the NEST protocol.

Data Transfer Plan

1. All surveys (OBP, NEST, QBASE, QPV, QTT and QFF) completed by MetroHealth will be done either on a CCF/IRB approved iPad or via a direct email link that will take the participant directly to REDCap and will be stored via the Cleveland Clinic REDCap database. Study participant documentation will be stored and maintained by MetroHealth and CCF
2. MetroHealth will use the same, CCF/IRB approved, audio recording devices and will store the audio on their secure drive for data storage in the same manner as CCF.
3. Once a weeks, a member of the CCF study staff will travel to MetroHealth. During this visit, the audio files on MetroHealth secure drive will be transferred via an encrypted jump drive provided by CCF to a CCF laptop. During this visit, **we will also obtain electronic copies of signed informed consents for all newly enrolled MetroHealth participants (OB providers, patients and partners) at that time.**
4. MetroHealth will only have CCF REDCap access to input data and see data via their user group. All other REDCap functions will be disabled.

CCF Procedures

Initial Provider Recruitment

1. Research coordinator will send an IRB approved recruitment letter to providers who meet inclusion criteria
 - a. [name], study P.I., will send follow up emails to providers
2. Distribute the OBP survey electronically through REDCap on CCF/IRB approved iPads

Initial Patient Recruitment

1. Chart review
2. Initial contact via MyChart or by email if sent through EPIC pool to patients who meet inclusion criteria
3. Obtain informed consent
 - a. If consented into direct observation: provide CCF/IRB approved audio recorder, once completed the file is immediately stored on secure drive for data storage
4. Distribute the initial survey(s) electronically through REDCap on CCF/IRB approved iPads

Initial Partner Recruitment

1. Partner will be offered enrollment with consent of patient on day of 1st OB visit if partner arrives with the patient.
2. Obtain informed consent
 - a. If consented into direct observation: provide CCF/IRB approved audio recorder, once completed the file is immediately stored on secure drive for data storage
 - b. Collect SSN, DOB and email for follow-up survey
3. Distribute the initial survey(s) electronically through REDCap on CCF/IRB approved iPads

Patient Follow-up(s)

1. Chart review, to be done prior to any communication
2. Send follow up surveys based on timeline:
 - a. QPV: 7-9 days after first OB appointment
 - b. QTT: 12-22 weeks of pregnancy (based on LMP)
 - c. QFF: 22-24 weeks of pregnancy (based on LMP)

Partner Follow-up

1. If patient's Chart review is viable use the email given with consent to send QPV 7-9 days after first OB appointment.

MetroHealth Procedures

Initial Provider Recruitment

1. Research coordinator will send an IRB approved recruitment letter to providers who meet inclusion criteria
 - a. [name], site P.I., will send follow up emails to providers
2. Distribute the OBP survey electronically through REDCap on CCF/IRB approved iPads

Initial Patient Recruitment

1. Chart review
2. Initial contact via MyChart or by text message or by email if prompted through phone scheduler questionnaire to patients who meet inclusion criteria
3. Obtain informed consent
 - a. If consented into direct observation: provide CCF/IRB approved audio recorder, once completed the file is immediately stored on secure drive for data storage to be collected by CCF
4. Distribute the initial survey(s) electronically through REDCap on CCF/IRB approved iPads

Initial Partner Recruitment

1. Partner will be offered enrollment with consent of patient on day of 1st OB visit if partner arrives with the patient.
2. Obtain informed consent
 - a. If consented into direct observation: provide CCF/IRB approved audio recorder, once completed the file is immediately stored on secure drive for data storage to be collected by CCF
 - b. Collect SSN, DOB and email for follow-up survey
3. Distribute the initial survey(s) electronically through REDCap on CCF/IRB approved iPads

Patient Follow-up(s)

1. Chart review, to be done prior to any communication
2. Send follow up surveys based on timeline:
 - a. QPV: 7-9 days after first OB appointment
 - b. QTT: 12-22 weeks of pregnancy (based on LMP)
 - c. QFF: 22-24 weeks of pregnancy (based on LMP)

Partner Follow-up

1. If patient's Chart review is viable use the email given with consent to send QPV 7-9 days after first OB appointment.

CCF Procedures

Audio transcriptions will be completed by the NEST study staff at CCF

All research stipends for patients (NEST [if applicable], QBASE, QPV, QTT & QFF) and partners (QBASE & QPV) will be sent through CCF

All gift cards for completion of the OBP survey (providers only) will be sent through CCF

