Per the original protocol, a database will be constructed using the EMR which will include patients' contact information, including MRN, DOB, mailing address, email address and telephone number(s), name of provider and date and place of upcoming prenatal appointment as described in the initial protocol. Initially, recruitment of patients was to take place by mailing a recruitment letter to eligible patients who are scheduled to see one of the providers at the recruitment sites for prenatal care. Given that the study entails identifying women's baseline

knowledge and health literacy with respect to genetics, heritable risk, and the fetal genetic risk assessment process at the first visit, the time to collect these data before the initial prenatal visit is limited. Contact for study recruitment needs to be made in the window before the initial prenatal visit where patients will discuss prenatal testing with their physician or midwife as part of the standard practice of obstetric care. This is a limited window as there is only a short interval of time between when a patient may schedule the initial prenatal visit (e.g., at 7-8 weeks EGA) and the time of her initial prenatal visit (e.g.; 9-10 weeks EGA). Because of this limited window, we therefore need a method of communication that allows for contact with patients who meet the study inclusion criteria in an expeditious manner.

Three options to contact the patients include use of 1) MyChart message, 2) EPIC NEST pool, 3) in person at the clinic visit and 4) Mailers

- 1) We will recruit participants using MyChart. We will recruit participants by sending an IRB-approved message via MyChart to eligible patients scheduled to see one of the study providers at the recruitment sites for prenatal care. The MyChart message will give a brief overview of the study, the benefits and risks, and give instructions to the patient to contact the Research Coordinator if interested in participation. The interested patient will be sent further information regarding the research study via email or postal mail, based on her preference.

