We will utilize a series of questionnaires to assess the study outcomes. This includes the questionnaires administered at different stages of pregnancy in addition to the intervention. These were developed by the following procedures:

[name] and her research team, with the input of the study Co-Investigators and members of the Advisory Panel, developed draft instruments based on existing validated instruments in the literature. Specific instruments include:

- (1) Multidimensional Measure of Informed Choice (MMIC), a validated tool that uses to multiple choice and Likert-scale items to measure knowledge, attitudes, and decision-making associated with prenatal genetic testing
- (2) Decisional Regret Scale (DSC), a validated scale using Likert-scale items to measure satisfaction/regret with the decision-making process (not the outcome of the decision).
- (3) Medical Term Recognition Test (METER), a validated tool used to assess health literacy. In METER, a list of 70 terms are given to a participant that contain some real medical words (i.e. words that have to do with body parts, body functions, types of diseases, etc.). The list also contains some items that may look or even sound like medical words but are not actually real words. The participant is given instructions to place an “X” next to the words they recognize to be real words. The participant is also told they should not guess and to only put an “X” next to a word if they are sure it is a real medical word.

Questionnaire development involved a process of modifying the MMIC. Because the MMIC developed several years ago, modifications were required to ensure that the instruments were able to assess primary and secondary outcomes. Initial survey items were developed through a consensus-building process among the study co-investigators. The instruments were then tested through a process of cognitive interviews (Amendment #1). The draft instrument was revised based on this process and then utilized for data collection. The finalized instruments were approved for use by the IRB (Amendment #5).

The data collection instruments are as follows:

- a. Baseline questionnaire (**QBASE**): This survey will collect the following information: (1) participant demographic and reproductive history information, (2) healthcare decision-making preferences, (3) participant knowledge and (4) familiarity with the concept of shared decision-making.

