- b. Post initial visit questionnaire (**QPV**): This survey will collect the following information: (1) participant knowledge, attitudes, and decision-making regarding NIPT (alternative tests or no testing), (2) health literacy.
- c. Time of testing questionnaire (**QTT**): This survey will collect the following information: (1) participant knowledge, attitudes, and decision-making regarding NIPT (alternative tests or no testing) and (2) decisional regret.
- d. Follow-up questionnaire (**QFF**) This survey will collect the following information: (1) participant knowledge, attitudes, and decision-making regarding NIPT (alternative tests or no testing) and (2) decision-making regret.

Measures	Baseline (QBase)	Post visit (QPV)	Time of test (QTT)	Follow up (QFF)
Demographics	X			
Shared decision-making and decision-making preferences	X	X	X	X
Informed choice/MMIC		X	X	X
Decisional regret/DSC			X	X

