to either (1) record the whole appointment. If this happens the research assistant will only transcribe the dialogue pertaining to prenatal genetic screening, or, (2) to turn on the recorder when the discussion regarding prenatal genetic screening is taking place.

As recent guidelines have changes, we will again be offering patients the option to consent to audio-recording during their first visit for the CCF and MetroHealth sites.

4) QPV: This survey will be administered approximately 7-10 days following the first visit when the basic concepts associated with prenatal genetic testing have been introduced. It will be administered using online REDCap survey. Unless otherwise specified by the participant.

5) QTT: This survey will be administered between weeks 12-22 EGA once the participant has made a decision about if to undergo prenatal genetic testing (or at the EGA at which the opportunity has closed in the case of those participants who elect against testing). It will be administered using online using REDCap survey. Unless otherwise specified by the participant.

6) QFF: This survey will be administered between weeks 22-24 EGA. It will be administered using online using REDCap survey. Unless otherwise specified by the participant.

A review of the medical record will be conducted prior to communication about each survey to ensure that the participant continues to meet inclusion criteria. Individuals who experienced a complication or fetal demise as documented at the time point of QPV, QTT and QFF, or who no longer receive care at the Cleveland Clinic or MetroHealth, depending on original site of enrollment and will not be contacted to complete the survey(s). Each study site, either Cleveland Clinic or MetroHealth, will be responsible for all subsequent chart reviews and administration of all QPV, QTT and QFF surveys for all participants enrolled at those sites. All patients will receive a research stipend of the following amounts for each of the completed surveys from the Cleveland Clinic Accounts Payable Offices (patients will receive up to \$150.00):

- 1) QBASE - \$25.00
- 2) QPV - \$25.00
- 3) QTT - \$50.00
- 4) QFF - \$50.00

II. Partners of participating pregnant patients

We will utilize the same data collection instruments and procedures at both the Cleveland Clinic and MetroHealth.

Data collection instruments: This includes the QBASE and QPV, both identical to the questionnaires administered to pregnant participants.

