Data from the surveys will be collected either 1) using a tablet PC enabled with REDCap Survey for direct data entry or, if necessary, due to technical issues 2) on paper surveys with manual entry by the research team into REDCap. This is only done if there is a technical issue with the iPads or printers (internet connectivity problems, battery issues, etc.).

The following analysis will be conducted with the Principal Investigator in conjunction with [name], the QHS statistician designated to the WHI using JMP and SAS:

Data from the direct observation will be analyzed using the *observed* OPTIONS scale. This is a validated scale similar to the *dyadic* OPTIONS scale but developed for direct observation measurement of SDM in the clinical encounter. The *observed* OPTIONS scale will be utilized in conjunction with a content checklist to determine if the information exchanged during discussions of prenatal genetic risk and assessment meets the needs and preferences of patients, the recommendations of OB providers and GCs published by the American College of Obstetricians and Gynecologists, and clinical practice guidelines. The checklist was developed using data from our preliminary studies.

Audio recordings from the direct observation will be transcribed verbatim for analysis. Transcriptions will be coded by two independent coders using the *observed* OPTIONS scale and content checklist. Measures will be analyzed as a function of exposure (NEST vs. control) and visit composition (patient only vs. patient/partner pairs). The content checklist will be utilized to assess discussion content and to determine fidelity to the intervention. Transcriptions will be time-stamped to determine the length of discussions pertaining to prenatal genetic risk and assessment in NEST vs. control groups. Tukey-Kramer comparisons will be made to adjust for multiple comparisons. The matrix of predictor variables of intervention, patient characteristics, including variables of baseline knowledge and attitudes, presence of partner at the visit, and provider characteristics will be examined using the co-linearity tests of variance inflation factors and condition indices. Those variables exhibiting sufficient independence will be included in the multivariable analysis. Kappa statistics will be calculated to assess the degree of agreement between the coders; a third coder will be brought in if consensus cannot be reached.

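### Health literacy is meant to be a pre-visit baseline measure but is scheduled only in the post-visit survey, so it follows the intervention and is missing for every woman without a QPV

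*Combined protocol and SAP*

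**What the plan says.** All references are to the combined protocol and SAP.

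- **Purpose (Recruitment Procedures, A. Cleveland Clinic).** The study is to establish women's baseline "knowledge and health literacy with respect to genetics, heritable risk, and the fetal genetic risk assessment process at the first visit". The same paragraph adds that "the time to collect these data before the initial prenatal visit is limited" and gives this as the reason for a faster means of contact.
- **Instrument (Data collection instruments and intervention).** The tool is the "Medical Term Recognition Test (METER), a validated tool used to assess health literacy", a list of 70 terms.
- **QBASE (item a).** The content is given as "1) participant demographic and reproductive history information, (2) healthcare decision-making preferences, (3) participant knowledge and (4) familiarity with the concept of shared decision-making". Health literacy is not listed.
- **QPV (item b).** The content is "participant knowledge, attitudes, and decision-making regarding NIPT (alternative tests or no testing), (2) health literacy". QTT and QFF do not list health literacy, and the measures table has no row for it.
- **Timing (Data collection procedures, item 4).** "This survey will be administered approximately 7-10 days following the first visit". The Patient Follow-up lists for both sites give 7-9 days.
- **Who is contacted (same section).** Women with a complication or fetal demise, and women who have left the health system where they enrolled, are not sent the later surveys.
- **Analysis (Data Analysis).** The candidate predictors include "patient characteristics, including variables of baseline knowledge and attitudes, presence of partner at the visit, and provider characteristics". Health literacy is not named, and no method for missing survey data is given.

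**The concern.** The protocol states a reason for measuring health literacy before the visit and then schedules the only measurement after it. A baseline characteristic should be recorded before exposure and for everyone enrolled. Here it comes after the intervention and depends on the return of a follow-up survey that is online by default.

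Three uses are affected:

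- **Arm comparability.** Practices, not women, are randomized, and imbalances are corrected manually, so patient characteristics at entry are worth checking. No literacy value exists at entry.
- **Non-response.** Literacy could plausibly affect survey return, and the recruitment section itself raises a digital divide. A measure held only by responders cannot describe non-responders.
- **Adjustment.** If literacy were used among the patient characteristics, some recorded visits would have no value.

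**Working it through.** The plan gives no figure on this point to reproduce. The check is a comparison of sections, followed by an illustration of size under stated assumptions.

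**1. Sequence of measurements**

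| Step | Arms | Health literacy listed? |
|---|---|---|
| QBASE, before the visit | both | no (0 of 4 components) |
| NEST, before the visit | intervention only | no |
| First visit, recorded with consent; primary outcome | both | not applicable |
| QPV, 7-10 (or 7-9) days after the visit | both | yes |
| QTT, weeks 12-22 | both | no |
| QFF, weeks 22-24 | both | no |

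The stated intent places the measure at or before the visit, and the schedule places it at least 7 days after. The interval runs from the visit. NEST may be completed online before the visit day, so the gap from NEST can be longer. No section schedules a literacy measure before the visit in either arm.

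**2. Who has a value**

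The primary outcome is fixed once the visit is recorded. METER exists only if the woman is still eligible for contact, is sent QPV and returns it. A woman can therefore have a primary outcome and no literacy value.

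**3. Size if METER were used as a covariate**

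The documents give no response rate, so the return proportion *r* among recorded women is an assumption. In a complete-case model the share of visits lost is 1 − *r*. With independent observations, the standard error grows by 1/√*r*:

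- *r* = 0.90: 10% lost, 1/√0.90 = 1.05
- *r* = 0.80: 20% lost, 1/√0.80 = 1.12
- *r* = 0.70: 30% lost, 1/√0.70 = 1.20

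If the losses are spread evenly over practices, these factors are upper guides, because the between-practice part of the variance does not grow.

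**4. What could not be seen**

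Suppose the probability of returning QPV is 1/(1 + exp(−(1.2 + *b*·*z*))), with *z* a standard normal literacy score. Both 1.2 and *b* are assumptions.

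- *b* = 0: return is 77% at every literacy level.
- *b* = 0.5: overall return 76%; 66% in the lowest literacy third, 85% in the highest.
- *b* = 1.0: overall return 73%; 53% in the lowest third, 90% in the highest.

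The overall rates are close, while the gradients range from none to steep. With METER inside QPV, the trial's data cannot tell these cases apart. With METER collected at entry, they could.

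**The case against.** **The construct may differ.** The recruitment section speaks of literacy about genetics and fetal risk, whereas METER tests recognition of general medical words. QBASE collects knowledge in both arms before the visit, so the phrase may be loose wording. This stands in part. However, that section lists knowledge and health literacy separately, METER is the only instrument labelled as a literacy measure, and NEST's familiarity items exist in one arm only.

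**No planned analysis names health literacy.** This stands. Patient characteristics are an open class in the Data Analysis section, so use is possible but not specified. Complete-case handling is also an assumption.

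**QBASE already supports other comparisons.** This stands. Demographics, reproductive history, decision preferences and knowledge can describe the arms at entry and QPV non-responders. Only the literacy part is lost. The background also names literacy as one of several difficulties in counselling, not the main one.

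**A stronger reading is that NEST raises METER scores and that adjusting for METER would remove part of the true effect.** For example, with a true effect of 0.30 SD, a METER-outcome correlation of 0.2 to 0.4 and a METER shift of 0.1 to 0.3 SD, the adjusted effect would fall to between 0.30 − 0.2 × 0.1 = 0.28 and 0.30 − 0.4 × 0.3 = 0.18. The documents do not support such a shift. NEST is described as asking about familiarity and priorities, and its report only presents the patient's own entries. It is not described as teaching medical vocabulary, and general literacy may change little in 7-10 days. With no shift there is no such bias.

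**Keeping a 70-term list out of a short pre-visit window is a defensible choice about burden.** That is fair, but the protocol does not make this argument; it says that literacy belongs in that window.

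**Conclusion.** The inconsistency is real, and no other section resolves it. Followed as written, the plan never takes the literacy measure before the visit, and takes it only from women who return QPV.

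The firm consequence is missing values: no literacy comparison of QPV responders with non-responders, and an incomplete patient characteristic if literacy enters the multivariable analysis. The extent is unknown. The range of 10% to 30% of visits lost rests wholly on the assumed return of 90% to 70% and on complete-case use of METER.

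A reader might infer that the primary analysis is biased or that the arms cannot be compared at entry. Neither follows. The primary outcome does not depend on METER, literacy is not a named covariate, and other baseline data are collected before the visit. This is a cheap improvement to the plan and does not threaten the main result.

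**What to change.** 1. For women enrolled from now on, move METER from QPV to QBASE in both arms and have it completed before NEST. Amend the QBASE and QPV descriptions to match the recruitment section, and add a health-literacy row to the measures table.
2. Check the order of forms. For virtual visits at MetroHealth, intervention women are told to complete NEST before QBASE, so moving METER into QBASE is not enough there; METER must be placed ahead of NEST.
3. Use the pre-visit value to describe arm comparability, to compare responders with non-responders at QPV, QTT and QFF, and as the literacy covariate if one is used.
4. For women already enrolled, label the QPV METER as a post-visit value, flag its timing, and use it in adjusted models only as a sensitivity analysis.

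The cost is one existing REDCap form moved and one amendment. The pre-visit survey becomes longer by 70 terms in a short window, most noticeably for intervention women, who also complete NEST. The cohort will have two measurement timings, and women already enrolled will have no baseline value. Partners receive surveys described as identical to the patients', so the amendment should say whether the move applies to them once their recruitment resumes.
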